4.2 STUDY TREATMENT

The investigational medicinal product (IMP) for this study is GDC-0853.

4.2.1 Formulation, Packaging, and Handling

GDC-0853 will be provided by the Sponsor as 50-mg dose strength tablets.

Tablets will be supplied in bottles, which will be appropriately labeled for this study. GDC-0853 tablets should be stored between 2°C (35.6°F) and 8°C (46.4°F).

For information on the formulation and handling of GDC-0853, see the GDC-0853 Investigator's Brochure.

4.2.2 Dosage, Administration, and Compliance

4.2.2.1 GDC-0853 Dose and Administration

The GDC-0853 dose regimen is oral 200 mg BID. Patients will receive GDC-0853 approximately every 12 hours for approximately 48 weeks. The first open-label dose of GDC-0853 should be the a.m. dose (taken in clinic) during the Week 48 visit of the GA30044 study (which is Day 1 of Study GA30066). Patients should be directed to take one dose (a total of 4 tablets) BID (total of 8 tablets each day). On clinic visit days when PK assessments are performed (Day 1 and Week 24), patients should be instructed that GDC-0853 will be administered in the clinic.

In general, a dosing window of ± 2 hours is acceptable. If a dose is taken more than 2 hours late or is missed altogether, the patient should resume normal dosing with the next scheduled dose. Patients should record on the bottle the dose that was missed and notify study staff of any missed doses. Doses that are vomited will be considered missed doses.

A dose reduction of GDC-0853 for specific safety events is permitted (see [Table 3](#)). For a potential dose reduction for other adverse events not listed in the table, please consult the Medical Monitor. If dose reduction is indicated, the dose of GDC-0853 may be reduced from 200 mg BID to 200 mg QD or lower (in consultation with the Medical Monitor). If the adverse event resolves and the patient has increased lupus disease activity, it is up to the discretion of the investigator in consultation with the Medical Monitor to decide if the patient can resume the 200 mg BID dosing.

Guidelines for dose reduction and treatment interruption or discontinuation are provided in Section 5.1.2.

GDC-0853 will be orally administered and may be taken with or without food except for the instances (see [Appendix 1](#)) where the dose of oral study drug is to be administered at the clinic visit while fasting (≥ 4 hours prior to the clinic visit). The dates and times of the most recent prior meal, last dose of GDC-0853 (prior to clinic visit), and timing of GDC-0853 administration in clinic should be recorded at clinic visits with PK and/or fasting lipid assessments. In addition, any use of PPIs, H₂-receptor antagonists (H₂RAs), and/or short-acting antacids (e.g., Maalox[®], Pepto-Bismol[®], Roloids[®]) should be recorded as concomitant medications, including time and date of last administration prior to the PK clinic visits. Administration of GDC-0853 should be staggered with short-acting antacid use (i.e., GDC-0853 should be taken 2 hours before or 2 hours after the short-acting antacid).

At study visits, sufficient GDC-0853 tablets will be dispensed to complete dosing until the next scheduled visit. When GDC-0853 is administered at the site, it will be administered under supervision of study personnel, and the amount of GDC-0853 dispensed must be recorded.

4.2.2.2 GDC-0853 Compliance

The following measure will be taken to assess patient compliance with study drug: Patients will be directed to bring any used and unused bottles to each visit.

Sites will be responsible for prepopulating the dates on the dosing label (that should be affixed to the bottle) for when patients are scheduled to take study drug. Under the corresponding dates listed, the patients will record the times (a.m. or p.m.) that they take each dose on the affixed label. Refer to [Appendix 6](#) for the bottle and label configuration. The number of tablets issued minus the number of tablets returned will be used to calculate the number of tablets taken and compliance.

Compliance will be documented on the source record.

Any overdose or incorrect administration of study drug should be noted on the Study Drug Administration electronic Case Report Form (eCRF). Adverse events associated with an overdose or incorrect administration of study drug should be recorded on the Adverse Event eCRF. If compliance is $\leq 80\%$, the investigator or designee is to counsel the patient and ensure steps are taken to improve compliance.

4.2.2.3 Background Standard of Care Therapy

4.2.2.3.1 Immunosuppressant Therapy

Patients should be encouraged to remain stable on their background therapies (e.g., antimalarials, immunosuppressants), but they will be allowed to change doses, discontinue, and/or switch to other permitted immunosuppressant therapies during the

OLE if clinically indicated (see Section 4.3.1). Certain doses and combinations of immunosuppressants are not allowed with GDC-0853 (see Section 4.3.2).

If dose modification (increase or decrease) of an immunosuppressant is required because of increased clinical disease activity or toxicity, this must be recorded as an adverse event on the Adverse Event eCRF, and the dose modification must be recorded in the Immunosuppressant Review eCRF.

Any overdose or incorrect administration of an immunosuppressant should be noted on the Immunosuppressant Review eCRF. Adverse events associated with an overdose or incorrect administration of an immunosuppressant should be recorded on the Adverse Event eCRF.

4.2.2.3.2 Corticosteroid

Patients who enter the OLE study on prednisone > 10 mg/day or equivalent OCS (see Appendix 2) should be encouraged to taper their OCS, with the goal of achieving an OCS dose of < 10 mg/day prednisone or equivalent. All steroid changes should be captured on the OCS diary (see Section 4.2.2.4).

Any change in steroid dose must be recorded on the Corticosteroid Medication eCRF.

It is recommended that all patients receiving corticosteroids should receive appropriate supportive therapy to help prevent steroid-induced osteoporosis (e.g., calcium, vitamin D supplements, bisphosphonates) as per local guidelines and physician preference. *Pneumocystis jiroveci* pneumonia prophylaxis is also recommended to be used as per local SOC.

4.2.2.3.3 Burst Treatment

In the case of increased disease activity, the patient will have the opportunity to receive burst treatment (defined as an increase or new dose of oral prednisone or equivalent), in addition to the study treatment. The patient should return to the clinic, either at a scheduled study visit or unscheduled flare visit, to be evaluated and to receive an increase or new dose of oral prednisone as follows:

- A burst is defined as an increase or new dose of oral prednisone up to 40 mg/day (or equivalent, see Appendix 2).

When using corticosteroids as a burst treatment, the investigator may temporarily increase the dose of corticosteroids, and then the investigator should attempt to taper the patient back down to his or her previous corticosteroid dose, ideally within 2 weeks. Patients will continue to receive their designated dose of study treatment (see Section 3.1) during the burst treatment. The previous corticosteroid dose is defined as the dose of corticosteroids taken prior to the burst. If the patient was not previously on corticosteroids, the investigator should attempt to taper the patient back off corticosteroids completely. If the patient was on a corticosteroid-tapering schedule at

the time of the burst treatment, the investigator will revise the tapering schedule as necessary to attempt to meet the target OCS dose (< 10 mg/day).

Any changes in steroid doses will be recorded in the Corticosteroid Medication eCRF.

Patients may receive corticosteroids for emergent illness other than SLE (e.g., trauma, asthma) or if clinically warranted to prevent adrenal crisis (e.g., prior to surgery). If possible, the additional corticosteroid treatment in these cases should last no more than 7 days. After resolution of the acute emergent illness, the patient should resume his or her standard OCS dose and taper regimen.

Any dose of steroid higher than the maximum burst levels above or any necessity for additional burst treatments for increased SLE-related activity (either a second treatment within the burst window or a burst treatment outside the burst window), as determined by the investigator, will be considered escape therapy (see Section 4.2.2.3.4) and will be recorded in the Corticosteroid Medication eCRF.

Use of burst therapy to treat worsening of lupus will be captured on the Adverse Event eCRF (see Section 5.3.5.9). If any patient needs additional corticosteroids for this or any other reason, the Medical Monitor needs to be informed and the reason recorded on the Corticosteroid Medication eCRF (see Section 4.2.2.3.4).

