3.3.4.2 Corticosteroid Taper

There is a substantial unmet need for effective corticosteroid-sparing treatments for SLE, and this study will assess the corticosteroid sparing potential of GDC-0853. Chronic corticosteroid use has many adverse short- and long-term consequences, so reducing corticosteroid doses in patients with SLE will decrease the incidence of short- and long-term comorbidities and potential adverse events, including in patients in this trial. The Glucocorticoid Toxicity Change Index (GTCI) ([Miloslavsky et al. 2017](#)) will be used to determine the potential of GDC-0853 to reduce steroid-induced systemic side effects (see [Appendix 3](#)). In addition, unrestricted use of corticosteroids in SLE clinical trials can confound safety and efficacy measurements and decrease the ability to detect the biologic activity/efficacy of the experimental drug ([Reddy et al. 2013](#)). Although the investigators can adjust steroids per their discretion based on SLE disease activity to best determine the safety and efficacy of GDC-0853, corticosteroids should be tapered as tolerated during the OLE, with a goal of < 10 mg/day prednisone or equivalent.

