4.2.2.3.4 Escape Therapy

If an increase in immunosuppressive therapy (referred to as “escape therapy”) is deemed medically necessary due to increased SLE disease activity, the patient will be given escape therapy, which will be recorded on the Immunosuppressant Review and/or Corticosteroid Medication eCRFs. Patients receiving the following escape therapies, after informing the Medical Monitor, will be allowed to remain on study drug but will be considered a protocol-defined “non-responder” in the secondary efficacy analysis:

- IV steroids
- OCS doses exceeding the limits described in Section 4.2.2.3.3
- New or increased doses of an immunosuppressant medication up to the maximum allowed in the study (see Section 4.3.1)

NOTE: Any combination of azathioprine, methotrexate, mycophenolate mofetil, or mycophenolic sodium is prohibited during the study while the patient is receiving study treatment (see Section 4.3.2).

Whenever possible, a patient being evaluated for escape therapy will undergo assessment at either an unscheduled or flare visit prior to the increase in immunosuppression in order to quantify and record the increased disease activity, unless this occurs at a scheduled study visit (see Appendix 1).

If the patient requires any further treatment for SLE activity beyond the escape therapy described above (e.g., prohibited medications as defined in Section 4.3.2 or any accepted immunosuppressant that exceeds the maximum dose as defined by the protocol or any increase in therapy not approved by the Medical Monitor), the patient should be discontinued from study treatment and return for the 8-week safety follow-up visit (see Section 4.5.1).

Use of escape therapy to treat worsening of lupus will be captured on the Adverse Event eCRF (see Section 5.3.5.9). If any patient needs additional corticosteroids for this or any other reason, the Medical Monitor needs to be informed and the reason recorded on the Corticosteroid Medication eCRF.

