4.4.6 Systemic Lupus Erythematosus Responder Index (SRI)

The SRI is a categorical assessment that evaluates disease activity in SLE based on the different organ systems. This index utilizes a combined evaluation of the BILAG-2004, SLEDAI-2K, and PGA (Sections, [4.4.5.1](#); [4.4.5.2](#); [4.4.5.6](#) to measure response to treatment. The SRI-4 primary endpoint defines response as meeting each of the following criteria at Week 48 compared with baseline:

- ≥ 4 point reduction in SLEDAI-2K score, and
- No new BILAG A organ domain score or two new BILAG B organ domain scores, and
- No worsening (worsening defined as a >0.3 point increase) in the PGA.

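### A first oral prednisone burst running at or shortly before Week 48 does not bar SRI-4 response, so response can be confounded with burst prednisone, and the burst window that might limit this is undefined

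*Combined protocol and SAP*

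**What the plan says.** **Burst (Section 4.2.2.3.3).** "A burst is defined as an increase or new dose of oral prednisone up to 40 mg/day" or equivalent. The investigator should attempt to "taper the patient back down to his or her previous corticosteroid dose, ideally within 2 weeks". This is an aim, with no binding end date. A dose above the maximum, or a need for additional bursts ("either a second treatment within the burst window or a burst treatment outside the burst window"), is escape therapy. No start, end or length of the burst window appears in the protocol.

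**Non-response (Section 4.2.2.3.4 and synopsis).** Patients given listed escape therapies may stay on study drug but "will be considered a protocol-defined “non-responder” in the secondary efficacy analysis". The list is IV steroids, "OCS doses exceeding the limits described in Section 4.2.2.3.3", and new or increased immunosuppressants up to the permitted maximum.

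**Endpoint (Section 4.4.6).** SRI-4 "defines response as meeting each of the following criteria at Week 48 compared with baseline". The criteria are a SLEDAI-2K fall of at least 4 points, no new BILAG A or two new BILAG Bs, and no PGA increase above 0.3. There is no steroid criterion, and the baseline visit is not named.

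**Steroid rationale (Section 3.3.4.2).** The protocol warns that "unrestricted use of corticosteroids in SLE clinical trials can confound safety and efficacy measurements". It sets a taper goal below 10 mg/day but lets investigators adjust steroids at their discretion.

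**Efficacy analysis (Section 6.5).** No steroid rule is given. Details are left to a data analysis plan that is not among the documents.

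**The concern.** SRI-4 at Week 48 is the secondary efficacy endpoint. A patient whose lupus worsens late in the study and is controlled with extra prednisone can reach the Week 48 visit meeting all three criteria. The written rule then counts a response, although the patient needed rescue for disease activity. A new or increased immunosuppressant given for the same worsening would make the same patient a non-responder. The study has one arm, so there is no comparator in which the same effect would also appear. Section 3.3.4.4 says the study is meant to show whether the drug improves response and/or reduces the need for systemic steroids. A response rate that is silent about steroid escalation near the endpoint answers that poorly.

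**Working it through.** The plan has no figure to reproduce: Section 6.1 states that no formal sample size calculation was done, and about 240 is an enrolment cap. The check is therefore a reading of the rules, followed by a labelled illustration.

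**1. Which steroid use changes responder status?**

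| Oral or IV steroid use for SLE | Status under the text |
|---|---|
| IV steroid | Non-responder (4.2.2.3.4) |
| Oral dose above 40 mg/day | Non-responder (4.2.2.3.3 with 4.2.2.3.4) |
| Second burst, up to 40 mg/day | Escape therapy (4.2.2.3.3). Non-responder if the limits cited in 4.2.2.3.4 include the number of bursts as well as the dose |
| Burst outside the burst window | Escape therapy, but cannot be identified because the window is undefined |
| First burst, up to 40 mg/day, running at Week 48 | No rule applies. Responder if the three items are met |

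**2. What does the look-back do?** SLEDAI-2K covers the visit and the preceding 28 days (Section 4.4.5.2, Appendix 10), and PGA covers the past 28 days (Section 4.4.5.6, Appendix 13). Week 48 is Day 337, and 337 − 28 = 309, which is Week 44. A flare active on or after about Day 309 is still scored at Week 48, even if prednisone has since cleared it. A flare treated and settled before Day 309 is not scored, even if the raised dose continues.

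A burst begun before Day 309 and still running on Day 337 has lasted more than 28 days, against the 14 days the protocol calls ideal. The text allows this but does not intend it. Appendix 1 schedules SLEDAI-2K, BILAG and PGA at Week 36 and next at Week 48, so any assessment between them depends on an unscheduled or flare visit, and SRI-4 does not use that visit.

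**3. BILAG.** Appendix 9 compares the last 4 weeks with the previous 4. A new episode that also meets the improvement criteria is recorded as improving instead of new. Those criteria require improvement large enough to consider reducing therapy, present now and for at least 2 of the last 4 weeks, or complete resolution for the whole of the last week. A burst inside the last 4 weeks can therefore change the BILAG entry, although the same flare still counts on SLEDAI-2K.

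**4. Internal comparison.** Appendix 11 scores prednisone above 0.5 mg/kg/day as a severe flare. Since 40 ÷ 0.5 = 80, a 40 mg/day burst passes that mark for any patient under 80 kg. The modification in Section 4.4.5.2 removes only the trigger of SLEDAI-2K above 12 alone. One patient can thus have a severe flare and be an SRI-4 responder.

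**5. Illustration of size (assumptions only).** Let b be the share of patients on a first burst at Week 48 and r the share of those who meet the three items. The number whose status depends on the gap is N × b × r, with N = 240.

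| b (assumed) | r = 30% | r = 70% |
|---|---|---|
| 2% | 1.4 patients, 0.6 points | 3.4 patients, 1.4 points |
| 5% | 3.6 patients, 1.5 points | 8.4 patients, 3.5 points |
| 10% | 7.2 patients, 3.0 points | 16.8 patients, 7.0 points |
| 15% | 10.8 patients, 4.5 points | 25.2 patients, 10.5 points |

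For scale, the 95% confidence half-width at an assumed 50% rate with N = 240 is 1.96 × √(0.25/240) = 6.3 points. The table counts reclassified patients. It does not estimate how many responded because of prednisone, since some would have met SRI-4 anyway.

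**The case against.** Four arguments on the other side have force.

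- **Bursts are limited.** A reader might infer that a burst is never escape therapy, whenever it is given. Section 4.2.2.3.3 says otherwise for a second burst and for one outside the burst window. It also caps the dose and asks for a return to the previous dose, so steroid use is not unrestricted in the sense of Section 3.3.4.2. This stands, and it confines the point to a first burst. It does not close the gap, because the timing clause depends on a window that is not defined.
- **The look-back partly protects the endpoint.** A reader might infer that a burst in the last 4 weeks improves all three components. For SLEDAI-2K and PGA, activity within the 28 days is still to be scored or rated. This stands. The exposed routes are the earlier burst still running, the BILAG improving rule, and a patient whose SLEDAI-2K remains at least 4 points below baseline despite the flare.
- **The objective is efficacy in combination with standard of care (Section 2).** A reader might infer that SRI-4 measures prednisone instead of GDC-0853. The documents do not support that. Without a concurrent control, drug, steroid and background effects cannot be separated under any scoring rule. Confounded with is the accurate description.
- **Burst use is visible elsewhere.** It enters the SFI, cumulative steroid dose, and the eCRFs, and the data analysis plan may already contain a steroid rule. The first part is true but changes no patient's responder status. The second cannot be checked, so the request is that the plan contain such a rule.

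**Conclusion.** The point holds in limited form. Under Sections 4.2.2.3.3, 4.2.2.3.4 and 4.4.6 together, a first oral burst of up to 40 mg/day at or shortly before Week 48 does not make a patient a non-responder, and SRI-4 has no steroid item. Response can therefore be confounded with burst prednisone. The one clause that could limit this by timing cannot be applied.

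The size is unknown. The assumed grid runs from 0.6 to 10.5 percentage points, but the documents support neither b nor r, so no value in it should be cited as the expected inflation. The most exposed case also requires the taper to overrun the ideal 2 weeks. The primary objective is safety and is unaffected. The point deserves correction because it bears on the secondary endpoint's interpretation and can be settled with data already being collected.

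**What to change.** 1. Leave burst treatment unchanged.
2. Reconcile the undefined burst window in Section 4.2.2.3.3 with the non-responder list in Section 4.2.2.3.4, so that it is clear which bursts count as escape therapy for the analysis and whether the cited limits cover number and timing as well as dose.
3. State which visit is the SRI-4 baseline. Section 4.4.6 does not say whether it is Day 1 of this study or the parent study's baseline.
4. Pre-specify a supplementary SRI-4 analysis, reported beside the main one. A patient is a non-responder if, in the 28 days before Week 48, the oral prednisone-equivalent dose was raised for SLE activity, or remained raised from an earlier burst, above either the pre-burst dose or the dose at the SRI-4 baseline.

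Both reference doses are needed. Comparison with Day 1 alone would miss, for example, a patient who entered on 20 mg/day, tapered to 5 mg/day and was then burst back to 20 mg/day. Steroids given for illness other than SLE do not count.

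The inputs exist: the OCS diary, the Corticosteroid Medication eCRF with the reason for additional steroid (Sections 4.2.2.3.2 to 4.2.2.4), and the dose equivalents in Appendix 2. The cost is clarifying wording in the protocol and analysis plan, one extra table, and a second response rate that will be slightly lower than the first.

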4.2.2.3.4 Escape Therapy

If an increase in immunosuppressive therapy (referred to as “escape therapy”) is deemed medically necessary due to increased SLE disease activity, the patient will be given escape therapy, which will be recorded on the Immunosuppressant Review and/or Corticosteroid Medication eCRFs. Patients receiving the following escape therapies, after informing the Medical Monitor, will be allowed to remain on study drug but will be considered a protocol-defined “non-responder” in the secondary efficacy analysis:

- IV steroids
- OCS doses exceeding the limits described in Section 4.2.2.3.3
- New or increased doses of an immunosuppressant medication up to the maximum allowed in the study (see Section 4.3.1)

NOTE: Any combination of azathioprine, methotrexate, mycophenolate mofetil, or mycophenolic sodium is prohibited during the study while the patient is receiving study treatment (see Section 4.3.2).

Whenever possible, a patient being evaluated for escape therapy will undergo assessment at either an unscheduled or flare visit prior to the increase in immunosuppression in order to quantify and record the increased disease activity, unless this occurs at a scheduled study visit (see Appendix 1).

If the patient requires any further treatment for SLE activity beyond the escape therapy described above (e.g., prohibited medications as defined in Section 4.3.2 or any accepted immunosuppressant that exceeds the maximum dose as defined by the protocol or any increase in therapy not approved by the Medical Monitor), the patient should be discontinued from study treatment and return for the 8-week safety follow-up visit (see Section 4.5.1).

Use of escape therapy to treat worsening of lupus will be captured on the Adverse Event eCRF (see Section 5.3.5.9). If any patient needs additional corticosteroids for this or any other reason, the Medical Monitor needs to be informed and the reason recorded on the Corticosteroid Medication eCRF.

